11.0 Data Management

- **Sample size and power:** The primary outcome for assessing differences between PENG+LFC vs. QL blocks will be postoperative cumulative opioid consumption (in IV morphine mg equivalents; IV MME) over time, up to 72 hours postoperatively. Cumulative opioid consumption will be evaluated in PACU, and at 12-hour intervals during the first 72 hours of the postoperative window. Differences in cumulative opioid consumption over time between block groups will be assessed using a linear mixed model approach. The model will include fixed effects for treatment group, postoperative time, and the interaction between block group and postoperative time and a random subject effect to account for correlation between measures collected on the same patient over time. Differences between block types at each postoperative time will be evaluated using linear contrasts from the model. A previous study⁹ conducted at MUSC found mean IV MME at 12 hours postop in subjects undergoing THA with a QL block was 16 ± 12 MME. A sample size of 48 subjects per group with 9 repeated measures of opioid consumption provides 80% power to detect a difference in cumulative MMEs consumed postoperatively of 4 MMEs at significance level $\alpha = 0.006$ (Bonferroni adjusted for 9 pairwise comparisons between group) assuming a standard deviation of ± 12 MMEs, a first-order autoregressive correlation structure and correlation between observations on the same subject of $\rho = 0.33$. We will plan to enroll 53 subjects/group (106 total) to allow for 10% attrition.
- Postoperative VAS pain score captured in the preoperative area, PACU and 12-hour intervals during the first 72 hours of the postoperative window will be collected as a secondary outcome and will be evaluated using a LMM similar to the primary outcome. Additional outcomes of interest include time to first ambulation, functional and mobility outcomes, PACU duration, patient satisfaction, and opioid related side effects.

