The participant will be asked to provide their average pain score while at rest, and average pain score with movement in the specified time period using a visual analog scale from 0-100 with 100 being the worst. The first pain score will be recorded before they leave the PACU on the day of the procedure. Beginning the following morning, the participant will receive a text message link sent by Twilio's secure server that opens a survey housed in RedCap. The first text message will arrive at 9:00 AM and will follow the schedule in **Table 1**.

The follow-up text messages will also ask the patient the name, dose, and frequency of any pain medication taken in that time period. On Day 7, the text message survey will assess functional outcomes by using two different questionnaires. The patient will schedule at least two post-operative in-person follow up visits as standard of care. One visit at approximately 2-3 weeks post-op, and the other at approximately 6 weeks.

During these two visits the patient will complete the same functional questionnaires as they did at Baseline and on Day 7. This may be done in person at their standard of care post-op visits or may be contacted by study personnel to complete via telephone. Adverse events will also be collected throughout the study.

The text messages are sent from a secure server, Twilio, and are housed in REDCap. The set of questions will state what time window (example: 12:00 AM midnight the night prior to 12:00 PM noon the same day) to consider when answering the questions.

If the participant has been discharged from the hospital, they will answer these questions in the text message each day. If they are admitted to the hospital at these points in time, the information will be gathered from their chart for medications and asked verbally for pain scores and additional questions. Additional data will be recorded by physical therapy and surgical staff and pulled from the patient's medical record for data collection.

If the participant is unable or unwilling to receive text messages, they will be provided a paper document to record their data for the pre-determined intervals so when a study member contacts them, they are able to relay their answers back accurately.

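### Opioid use is collected window by window but modelled as a running total, so after one skipped text every later total is unobserved and later answers cannot be used

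*Combined protocol and SAP*

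**What the plan says.** Section 11.0 defines the primary outcome as "postoperative cumulative opioid consumption (in IV morphine mg equivalents; IV MME) over time, up to 72 hours postoperatively", and the primary analysis is on that scale: "Differences in cumulative opioid consumption over time between block groups will be assessed using a linear mixed model approach". The model has group, time, their interaction and a random subject effect, with contrasts at each time. A first-order autoregressive structure appears only among the power assumptions.

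Section 10.0 describes how the data are obtained: "The follow-up text messages will also ask the patient the name, dose, and frequency of any pain medication taken in that time period". Table 1 has one record before discharge on the day of surgery and then six texts, POD 1-AM to POD 3-PM, covering separate, consecutive windows. Section 5.0 limits the trial to planned same-day discharge or observation of at most 23 hours, so most of these windows fall at home.

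Three provisions bear on incomplete data. While a patient is admitted, medication is taken from the chart. A patient who cannot or will not receive texts gets a paper record (both section 10.0). Data are used up to withdrawal of consent (section 13.0). The only numerical allowance is in section 11.0: "We will plan to enroll 53 subjects/group (106 total) to allow for 10% attrition". Nothing is said about a text that goes unanswered.

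**The concern.** A running total at a given time is the sum of all windows up to that time. If the POD 1-PM text is skipped, the totals from that window on are unobserved, even if the four later texts are all answered. Because each text asks only about its own window, a later reply does not recover the missing amount.

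A model fitted to running totals therefore cannot use the answers given after the gap. Since no rule is stated, the choice between dropping those totals, filling the gap or going back to the patient would be made during the conduct of the trial or at analysis. Precision at the later times is at stake. So is bias, if patients in more pain or more sedated are the ones who skip texts, or if response differs by group.

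**Working it through.** **The plan's own figure.** Inputs from section 11.0: difference 4 MME, SD 12, nine measures, AR(1) with ρ = 0.33, α = 0.006, power 80%. Two-sided testing is assumed.

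- SD of the nine-measure average: 12 × √{[9 + 2 Σ(9−k)·0.33^k, k = 1 to 8]/81} = 12 × √0.2024 = 5.40.
- n per group = 2 × 5.40² × (2.748 + 0.842)²/4² = 46.9, so 47. With α = 0.05/9 it is 47.6, so 48. The stated 48 reproduces.
- Enrolment: 48 × 1.10 = 52.8, so 53. (48/0.90 = 53.3 would give 54.)

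The 48 thus belongs to an average over nine measures, with each patient either present or lost.

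**Patients with all six texts answered.** If each text is answered with probability p, independently, the share is p^6. The values of p are assumptions.

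| p | p^6 | of 53 per group |
|---|---|---|
| 0.99 | 0.941 | 49.9 |
| 0.98 | 0.886 | 46.9 |
| 0.95 | 0.735 | 39.0 |
| 0.90 | 0.531 | 28.2 |

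Keeping 48 of 53 complete needs p ≥ (48/53)^(1/6) = 0.984.

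Two things soften this:

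- *Clustering.* If misses cluster within patients (beta-binomial, intraclass correlation 0.5), 5% missed leaves 46.8 of 53 and 10% leaves 41.2.
- *Other sources.* If two early windows come from the chart, four texts are at risk: 0.95^4 = 0.81 and 0.90^4 = 0.66, or 43 and 35 of 53.

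**Effective number for the 72-hour total.** Completer counts overstate the loss, because the mixed model keeps the totals before the gap. The information loss was therefore computed directly. Assumptions: seven windows (PACU always observed, six texts missed independently), equal window SDs, and window correlation 0.2-0.7, either exchangeable or AR(1).

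- Let Σ be the window covariance. The variance of a fully observed total is V₀ = 1′Σ1.
- For missingness pattern m with probability π_m and selection matrix P_m, the information per patient is Σ_m π_m P_m′(P_m V P_m′)⁻¹P_m. Inverting it gives the variance V₁ of the estimated 72-hour mean. The effective n is 53 × V₀/V₁.
- Running-total model: V = LΣL′, with L the cumulative-sum matrix, and each pattern cut off at the first missed text.
- Window model: V = Σ, every answered window kept, and the seven means summed.
- Random intercept only: constant variance and equal correlation are used as working weights for the running totals, with a robust (sandwich) variance under the true LΣL′.

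| Model | 5% missed | 10% missed |
|---|---|---|
| Running totals, well-specified covariance | 46-52 | 39-50 |
| Running totals, random intercept only | 44-45 | 35-37 |
| Consumption per window | 52-53 | 50-53 |

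The lower ends come from AR(1) with correlation 0.2, and the upper ends from exchangeable correlation 0.7. The random intercept does worst because running totals grow in variance and neighbouring totals are highly correlated, which that structure cannot represent.

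**The case against.** The strongest reply is that a likelihood-based mixed model already handles missing outcomes under missing at random, so patients with gaps stay in the analysis. That stands. With a suitable covariance and 5% missed, the loss is small. But section 11.0 names only a random subject effect, and no covariance lets a model of running totals use what was reported after the gap.

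The chart and the paper record also reduce the number of windows at risk. Neither covers a discharged patient who accepts texts and skips one.

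Three stronger readings are tempting, and the documents do not support them:

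- A reader might infer that far fewer than 48 per group *will* have usable data. No response rate is given; at 98-99% response the allowance roughly suffices. The 39 and 28 are completer counts, and the planned analysis is not a completer analysis.
- A reader might infer that the 72-hour comparison was powered at 48 and now falls short. The 48 reproduces only for the nine-measure average. At a single time, 48 per group has about 13% power for 4 MME with SD 12 at α = 0.006. That is a separate matter, so 48 is not a like-for-like benchmark for the effective numbers above.
- A reader might infer that missed windows will be counted as zero. The plan is silent. Zero-filling at 10% missed would understate the total by about 9% (0.10 × 6/7 with equal window means), but nothing prescribes it. Imputation or staff follow-up would fit the text equally well.

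**Conclusion.** The mismatch is real and should be corrected. The plan collects consumption per window, models running totals, and has no rule for a skipped text; a per-patient attrition allowance does not cover non-response to single texts.

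The size is conditional. It rests on an assumed response rate, independent misses, equal window SDs and window correlations of 0.2-0.7. Under these, the random-intercept model on running totals gives up about 8-9 of 53 patients' worth of information on the 72-hour total at 5% missed and 16-18 at 10%. A window-level model gives up at most about 3. At 98-99% response, or with strongly clustered misses, the loss is modest. The case for change does not depend on the worst figures, since the alternative estimates the same cumulative differences and uses every answer.

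**What to change.** - **Model.** Fit the primary linear mixed model to consumption in each window, with group, window, their interaction and a covariance that allows window-specific variances. An unstructured matrix for seven windows has 7 × 8/2 = 28 parameters; name a simpler heterogeneous structure as the fallback.
- **Contrasts.** Obtain each cumulative difference as the sum of the window contrasts up to that time, with its standard error from the model. The cumulative outcome stays as planned.
- **Missed windows.** State that a missed window is missing and is never counted as zero.
- **Recovery.** Let the next survey reopen any unanswered window.
- **Sensitivity.** Add a simple analysis in which missed windows are given higher consumption than the model predicts, including by different amounts in the two groups.

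The cost is SAP wording and a REDCap branching question. There are two downsides: a reopened window has a longer recall period, and the window-level model still assumes missing at random, which is why the sensitivity analysis is needed. Multiple imputation by window would be an acceptable alternative if specified in advance.

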5.0 Inclusion and Exclusion Criteria/ Study Population

Inclusion Criteria

- Age greater than or equal to 18 years old
- Ambulatory patients undergoing elective hip arthroplasty (planned same day discharge or observation 23 hours or less)

Exclusion Criteria

- Local anesthetic allergy
- Subjects with a weight less than 40kg
- Subjects that are unable or choose not to give informed consent
- Known preoperative substance abuse

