10.0 Study Design / Methods

- **Objective and outcomes:** Determine if PENG+LFC blocks reduce opioid consumption compared to a QL block after THA.
- **Design:** This prospective, blinded clinical trial will randomize subject to receive a PENG+LFC or QL block prior to THA. The randomization will be created by a statistician prior to subject enrollment.
- **Groups:** Subjects will be randomized to receive a preoperative PENG+LFC (n=53) or QL (n = 53) block prior to THA.
- Potential participants that are on the operating room schedule for THA will be screened for eligibility via chart review.

Baseline

- Once subjects have signed an informed consent, they will be assigned an enrollment number. Randomization will be created prior to the study starting with half of the research subject numbers being assigned to receive a PENG+LFC block, and the other half assigned to receive a QL block. Both blocks are considered our current standard of care. A study team member will open the envelope labeled with the subject's assigned study ID to reveal the randomization assignment.

- The participant's medical record will be reviewed for demographic data collection and durations (operative, PACU, hospital stay).
- Before placing the block, participants will be asked what their current pain score is by using a Visual Analog Scale (VAS) from 0-100, and complete the HOOS Jr, and PROMIS-10 Global Health questionnaires.

Randomization

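### The primary opioid model adjusts for no baseline variable, although pre-block pain is already collected; the cost is precision only, and its size depends on a correlation the plan does not give.

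*Combined protocol and SAP*

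**What the plan says.** Section 11.0 (Data Management) contains the only description of the primary analysis. On the fixed part it states: "The model will include fixed effects for treatment group, postoperative time, and the interaction between block group and postoperative time". The random part is "a random subject effect to account for correlation between measures collected on the same patient over time". The comparisons are then drawn time by time: "Differences between block types at each postoperative time will be evaluated using linear contrasts from the model". No baseline covariate and no adjusted sensitivity analysis appear anywhere, and Sections 9.0 and 10.0 describe a 1:1 list with no stratification factor.

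The baseline information is in Section 10.0. Before the block, "participants will be asked what their current pain score is by using a Visual Analog Scale (VAS) from 0-100", and HOOS Jr and PROMIS-10 are completed; Table 2 repeats these items and adds quadriceps strength. Section 11.0 uses the preoperative VAS only as one time point of the secondary pain outcome. The chart review is described narrowly: the "medical record will be reviewed for demographic data collection and durations", the durations being operative, PACU and hospital stay. Preoperative opioid use is not listed.

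In Section 5.0 the only exclusion that bears on prior opioid exposure is "Known preoperative substance abuse".

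**The concern.** Pain before surgery and opioid use before surgery may both predict how much opioid a patient takes afterwards. For prior opioid use the link may be partly built into the outcome. The follow-up messages ask about all pain medication taken, and no rule separates a continuing home prescription from opioid taken for surgical pain.

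If such a predictor is left out of the model, the variation it explains stays in the error term of the group comparison, and any chance imbalance in it stays in the estimate. The random subject effect does not help: it describes correlation within a patient and removes no between-patient variation from a comparison of randomised groups. What is at stake is the width of the confidence intervals and the power, using a variable the trial already pays to collect.

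**Working it through.** **Inputs from Section 11.0.** 48 evaluable per group, nine repeated measures, a difference of 4 MME, SD 12 MME, first-order autoregressive correlation with ρ = 0.33, alpha 0.006 (0.05/9 = 0.0056, rounded), power 80%. Sidedness is not stated; two-sided is used because it reproduces the plan's figure.

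**Input not in the documents.** The correlation r between a baseline covariate and the outcome. A range of 0.1 to 0.5 is assumed.

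**Step 1: reproduce the plan's figure.** The claim is "A sample size of 48 subjects per group with 9 repeated measures of opioid consumption provides 80% power". It reproduces if the target is the difference averaged over the nine measures.
- Variance factor for a patient's mean: Σρ^|i−j| / 81 = 16.395 / 81 = 0.2024.
- SD of a patient's mean: 12 × √0.2024 = 5.40 MME.
- Standard error of the difference: 5.40 × √(2/48) = 1.10 MME.
- Power: Φ(4/1.102 − 2.748) = Φ(0.88) = 81.1%, with 47 per group needed for 80%. At alpha = 0.05/9, power is 80.4% and 48 per group are needed.

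There is no covariate in this calculation. Compound symmetry (42.9%) and one-sided alpha 0.006 (86.8%) do not reproduce the stated power.

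**Step 2: add a covariate.** Adjusting for a covariate with correlation r to the patient's mean multiplies the residual variance by (1 − r²). Power becomes Φ(4 / (1.102 × √(1 − r²)) − 2.748).

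| r (assumed) | variance removed | power at 48 per group | n per group for 80% |
|---|---|---|---|
| 0 | 0% | 81.1% | 47 |
| 0.1 | 1% | 81.6% | 47 |
| 0.2 | 4% | 83.1% | 46 |
| 0.3 | 9% | 85.5% | 43 |
| 0.4 | 16% | 88.7% | 40 |
| 0.5 | 25% | 92.6% | 36 |

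**Step 3: the comparison at a single time.** Here the SD is 12, the standard error is 12 × √(2/48) = 2.45 MME, and r is the correlation with the outcome at that time.
- Power for 4 MME: Φ(4/2.449 − 2.748) = Φ(−1.11) = 13.2%. With adjustment it is 15.0% at r = 0.3 and 19.4% at r = 0.5.
- Difference detectable with 80% power: (2.748 + 0.842) × 2.449 = 8.8 MME. With adjustment it is 8.4 MME at r = 0.3 and 7.6 MME at r = 0.5.

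**Step 4: chance imbalance.** A one-standard-error imbalance in the covariate shifts a single-time contrast by r × 12 × √(2/48): 0.24 MME at r = 0.1, 0.73 at r = 0.3 and 1.22 at r = 0.5.

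**The case against.** The strongest reply is that nothing here is an error. Allocation is randomised, so the unadjusted contrast is unbiased, its type I error is valid, and chance imbalance is already reflected in its standard error. The planning SD of 12 carries no stated adjustment, so the sample size and the model agree with each other. Covariate adjustment is discretionary, and every figure for its benefit rests on an assumed r; at r = 0.1 the gain is negligible. All of this stands. It limits the point to precision but does not remove it: a plausible predictor is collected before the block and is not used in the primary analysis.

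Three stronger readings are tempting, and the documents do not support them.
- *A few more opioid users in one arm could shift the result by about the 4 MME target.* The documents give neither the prevalence of prior use nor the excess consumption of users. Suppose 10% are users, each consuming 16 MME more. Three extra users in an arm of 53 then move its mean by 16 × 3/53 = 0.9 MME. A 4 MME shift needs 4 × 53/16 = 13.25 extra users, when only 0.10 × 106 = 10.6 are expected in the whole trial. A much larger excess, say 16 MME on each of three days (48 MME), would bring this down to 4 × 53/48 = 4.4 users, but that too is pure assumption.
- *Admitting opioid users adds a known amount to the variance.* The same assumptions give 0.1 × 0.9 × 16² = 23 on top of 144. But the SD of 12 comes from earlier hip arthroplasty patients with a QL block at the same institution, and that sample may already have included opioid users.
- *Prior opioid use will be available from the planned chart review.* That review is described as covering demographics and durations only.

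That prescribed opioid users can be enrolled is itself inferred from the absence of an exclusion; it is the plain reading, but not an explicit statement.

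**Conclusion.** The point holds as a missed gain in precision, not as a flaw in validity. The primary model has no baseline covariate, pre-block VAS is available at no extra burden, and nothing in eligibility or allocation controls prior opioid use. The gain in power for the time-averaged difference runs from half a percentage point at r = 0.1 to 11.5 points at r = 0.5 (92.6 − 81.1). The documents do not show where in that range VAS or prior opioid use would fall. The figures assume a linear covariate effect, ignore the small loss of degrees of freedom, and take the plan's nine measures as given.

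Adjustment should not be read as a remedy for the mismatch between the power calculation and the tests. The calculation claims that the sample size "provides 80% power to detect a difference in cumulative MMEs consumed postoperatively of 4 MMEs", which reproduces for an average over time, while the planned tests are at each time. Power for 4 MME at a single time is about 13%, and still below 20% at r = 0.5. That is a separate matter.

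**What to change.** Before unblinding, prespecify pre-block VAS as a fixed effect, together with its interaction with time, in the primary linear mixed model. The interaction matters because the outcome accumulates and is tested at each time: a single coefficient would subtract the same amount early and late, whereas a predictor's effect on cumulative use would be expected to grow. The single-time gains shown above generally need it. Keep the unadjusted model as a prespecified sensitivity analysis.

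Optionally, add preoperative opioid use (yes/no, or daily MME) as a new item in the medical record review and include it in the same way. Without it, an imbalance in prior use could be neither shown nor adjusted for.

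The cost is a few degrees of freedom (one slope per time point for each covariate, if time is categorical), a line or two of model specification and, for the optional item, a small amount of chart abstraction. Eligibility, visits and care do not change. The covariates need to be fixed in advance, because choosing them after results are known would invite a charge of selection.

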4.0 Study Endpoints

- The primary outcome will be postoperative cumulative opioid consumption (in IV morphine mg equivalents: IV MME) over time, up to 72 hours postoperatively. Cumulative opioid consumption will be evaluated at in PACU, and through 72 hours post-op.
- Secondary outcomes: Postoperative pain score measures on the visual analog scale (VAS) captured in the preoperative area, PACU, and through 72-hours post-op.
- Additional outcomes of interest include time to first ambulation, functional and mobility outcomes, PACU duration, patient satisfaction, and opioid related side effects.

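### The primary model for cumulative opioid use specifies only a random subject effect, so per-time contrasts share one standard error, and the stated 80% power belongs to a time-averaged difference, not to those contrasts

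*Combined protocol and SAP*

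**What the plan says.** Section 4.0 defines the primary outcome as "postoperative cumulative opioid consumption (in IV morphine mg equivalents: IV MME) over time, up to 72 hours postoperatively", and section 11.0 (sample size and power) repeats it. On timing, section 11.0 states: "Cumulative opioid consumption will be evaluated in PACU, and at 12-hour intervals during the first 72 hours of the postoperative window".

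The analysis is a linear mixed model whose fixed part has group, time and their product term. For the dependence within a patient it names one term only: "a random subject effect to account for correlation between measures collected on the same patient over time". The treatment comparison is then described: "Differences between block types at each postoperative time will be evaluated using linear contrasts from the model". No residual covariance structure, time-specific variance or robust standard error is given.

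The same paragraph holds the power statement: 48 per group, nine repeated measures, 80% power for 4 MME, alpha 0.006 (Bonferroni for nine between-group comparisons) and SD 12. The SD matches an earlier institutional result, "mean IV MME at 12 hours postop in subjects undergoing THA with a QL block was 16 ± 12 MME". The correlation assumption is "a first-order autoregressive correlation structure and correlation between observations on the same subject of" 0.33. This autoregressive structure is a planning input; it is not named as part of the analysis model.

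**The concern.** A random subject effect with ordinary residuals implies one variance at every time and one correlation between any two times. A running total does not behave that way. It starts small in PACU and adds a non-negative amount in each window, so its spread normally widens. Contrasts at single times then borrow a standard error from the average time. Early comparisons lose power, including the one at 12 hours, the only time with a planning SD. Late comparisons get intervals that are too narrow. Autoregressive residuals with one common variance would not help, because the variance would still be the same at all times.

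The power statement has a related problem. It uses the alpha for the separate comparisons, so a reader will take 80% as the power of each per-time contrast. If it instead refers to an average over all times, it does not describe the tests that will be reported.

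**Working it through.** **1. Reproducing the stated power.** Inputs from section 11.0: n = 48 per group, difference 4, SD 12, nine measures, AR(1) with rho 0.33, alpha 0.006 (taken as two-sided; critical value 2.748).

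- The variance of one subject's mean over nine measures is 144 times the mean of the 9×9 correlation matrix: 144 × 0.2024. SD = 12 × √0.2024 = 5.40.
- SE of the difference = 5.40 × √(2/48) = 1.102; 4/1.102 = 3.63.
- Power = Φ(3.63 − 2.748) = 81.1% (79.1% by noncentral t). This matches the stated 80%.

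Other readings at alpha 0.006 do not match: one-sided 86.8%; compound symmetry with nine measures 42.9%; AR(1) with seven measures 69.0%; a single-time contrast 13.2%.

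**2. Power of the contrast that will be tested.**

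- SE at one time with SD 12 = 12 × √(2/48) = 2.449; 4/2.449 = 1.633.
- Power = Φ(1.633 − 2.748) = 13.2% (12.6% by t). Correlation between times does not enter.
- Difference detectable with 80% power = (2.748 + 0.842) × 2.449 = 8.8 MME.

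**3. Is the planning structure plausible for a running total?** With a constant SD of 12 and lag-one correlation 0.33, the amount used in a window has SD √(2 × 144 × 0.67) = 13.9. Its correlation with the total so far is −0.67 × 12/13.9 = −0.58, so patients who had used more would have to use markedly less next. Changing only rho, averaged-difference power falls to 36% to 38% at 0.7 and 18% to 19% at 0.9.

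**4. What the analysis model does to the standard errors.** With balanced data, the random-intercept model uses the mean of the time-specific variances for every contrast. One fit to simulated skewed running totals confirmed this: SE 2.357 at all seven times, while time-specific SEs ran from 1.546 to 2.875.

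Assumptions, because the documents give no later SD: seven times (PACU as first window, then six), complete data, n = 48 per group, SD 12 at 12 hours, window variance constant or falling by up to 60% per window, between-window correlation 0 or 0.33. Worked example, constant and uncorrelated: each window has variance 144/2 = 72, so the total after k windows has variance 72k. The mean over seven times is 72 × 4 = 288, SD 17.0, and the model SE is 17.0 × √(2/48) = 3.46. The correct SEs are 1.73 (PACU), 2.45 (12 h) and 4.58 (72 h).

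With r = model SE / correct SE, 95% coverage is 2Φ(1.96r) − 1 and size is 2[1 − Φ(2.748r)]. Power at 12 h for a true 8 MME is Φ((8 − 2.748 × model SE)/2.449); with the correct SE it is 70%.

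| Pattern | Model SE | Correct SE at PACU / 72 h | 95% coverage at 72 h | Size at 72 h (nominal 0.006) | Power at 12 h for 8 MME | Family-wise error |
|---|---|---|---|---|---|---|
| Variance falling 60% per window, correlation 0 (mildest) | 2.54 | 2.07 / 2.67 | 94% | 0.009 | 66% | 0.013 |
| Constant variance, correlation 0 | 3.46 | 1.73 / 4.58 | 86% | 0.038 | 27% | 0.048 |
| Constant variance, correlation 0.33 (most extreme) | 4.58 | 1.50 / 6.86 | 81% | 0.067 | 3% | 0.067 |

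Across all ten patterns, the SD at 72 h is 13 to 34 MME, coverage at PACU is 98% to 100%, and size at PACU is below 0.001. Family-wise error over seven contrasts (40,000 simulated null trials per pattern) was at or below about 0.05 in nine of the ten. With time-specific variances, size was 0.005 to 0.007 at every time and family-wise error 0.014 to 0.024.

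**The case against.** The strongest reply is that the plan is silent, not wrong. It lists what the model will include and does not say that nothing else enters. Time-specific residual variances or a sandwich standard error would be compatible with the text, and either would remove the common SE. That is fair, but the plan commits to neither, and the model as stated has the defect. Leaving the choice open until the data are seen is a weakness in itself.

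Second, identical SEs are exact only with complete data, and 10% attrition is expected. With missing visits the SEs would differ somewhat, but they still would not follow the true variances.

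Third, the size of the harm is assumed. The worst values give the PACU stay the same variance as a 12-hour window, and the clock-time windows in Table 1 make even the 12-hour point approximate. The 8 MME used for the power loss is illustrative; the plan's own difference is 4. This limits how firmly any one figure can be held. The direction needs only that variance grows.

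Fourth, 13% is exact only where the SD is 12. Under the ten patterns with correct SEs, power for 4 MME is 21% to 47% at PACU, 13% at 12 h and 2% to 11% at 72 h. None of these is near 80%. That the 80% refers to an average is inferred from the reproduction; the plan does not say so.

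**Conclusion.** The concern holds on both counts and should be fixed.

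As written, the primary model gives per-time intervals that are too wide early and too narrow late, provided the variance of the running total grows with time. The extent depends on late SDs that the documents do not give, and ranges from slight to serious. Gross inflation of trial-level error is not the problem; misleading inference at individual times is.

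The planning finding depends on none of those growth assumptions. With the plan's own inputs, 80% is recovered only for a time-averaged difference, while a contrast at a time with SD 12 has about 13% power for 4 MME.

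**What to change.** Keep the fixed effects and the per-time contrasts. In section 11.0:

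1. Replace the random subject effect with an unstructured within-subject covariance over the scheduled times, with Kenward-Roger degrees of freedom. State in advance a fallback that still lets the variance differ by time, for example heterogeneous AR(1), if the model does not converge.
2. Restate the power for the contrast that will be tested, using time-specific SDs of cumulative MME from the earlier institutional data. If power for an averaged difference is also quoted, label it as such and support its correlations from the same data.
3. Settle the number of analysis times first. PACU plus six 12-hour points makes seven, while the power statement uses nine.

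The cost is wording only, with no new data and no change in enrolment. Unstructured covariance needs 7 × 8/2 = 28 parameters for about 96 patients (9 × 10/2 = 45 if nine times are meant), hence the fallback. The stated power will look less favourable.
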